### Formal Classification per the ICD-3

The following section is included as an indicator of the issues and severity that is commonly observed in subjects with trauma-related nightmares. For a subject to actually receive a diagnosis of nightmare disorder 2 is exceedingly rare. Having a diagnosis of nightmare disorder 2 is NOT a requirement for inclusion into this study. The third edition of the International Classification of Sleep Disorders states the following minimum criteria for nightmare disorder 2:

1. Repeated occurrences of extended, extremely dysphoric, and well-remembered dreams that usually involved threats to survival, security, or physical integrity.
2. On awakening from the dysphoric dreams, the person rapidly becomes oriented and alert.
3. The dream experience, or the sleep disturbance produced by the awakening from it, causes clinically significant distress or mental impairment in social, occupational or other important areas of functioning as indicated by the report of at least one of the following:
  - a. Mood disturbance (e.g., persistence of nightmares affects anxiety, dysphoria).
  - b. Sleep persistence (e.g., bedtime anxiety, fear of sleep/subsequent nightmares).
  - c. Cognitive impairments (e.g., intrusive, nightmare imagery, impaired concentration, or memory.)
  - d. Negative impact on caregiver or family functioning (e.g., nighttime disruption).
  - e. Behavioral problems (e.g., bedtime avoidance, fear of the dark).
  - f. Daytime sleepiness.
  - g. Fatigue or low energy.
  - h. Impaired occupational or educational function.
  - i. Impaired interpersonal/social function.

While it is commonly thought that nightmares emerge from REM sleep, nightmares have also been observed to emerge from Non-REM sleep. In a cohort of 35 subjects that suffered from PTSD, an almost equal percentage of subjects were documented to have NREM and REM related nightmares. Heart rate and respiratory rate accelerations have been observed with subjects arising from nightmares. Motor behaviors preceding nightmare awakenings have been observed in stage N2 sleep.

### **Prazosin Pharmacologic Therapy**

Prazosin is an  $\alpha_1$ -adrenergic receptor antagonist. This medication was originally intended for use as an antihypertensive. It is believed that Prazosin can be effective in the treatment of nightmares related to post-traumatic stress disorder by reducing noradrenergic activity in the brain; which has been found to be elevated in people diagnosed with PTSD. While some evidence supports the efficacy of Prazosin in treatment of nightmares in PTSD subjects, that evidence is inconsistent, not strong, and there are common side effects that raise concern including: dizziness, headache, drowsiness, lack of energy, weakness, palpitations, and nausea. Even more concerning is the risk of orthostatic hypotension, and the potential for syncope-related injury. The American Academy of Sleep Medicine suggests that clinicians monitor patients for potential orthostatic hypotension when prescribing Prazosin for nightmares.

### **Image Rehearsal Therapy**

Image rehearsal therapy is a form of cognitive behavioral therapy in which the subject later recalls a nightmare, then consciously imagines changes in the theme, storyline, ending, or any part of the dream, to a more positive and tolerable one. The intended outcome would be that when a subject has the rehearsed dream during sleep, they will replace the disturbing content with the positive and tolerable content imagined during the day. The subject will commonly practice the rehearsal of these dreams for 10 - 20 minutes per day. While this has been demonstrated to be generally effective in the treatment of nightmare disorder in subjects with PTSD, reports have described increased nightmare frequency and exacerbation of PTSD symptoms during image rehearsal therapy. Likewise, sleep logs that subjects use to document the frequency and content of nightmares have been associated with subject reluctance to fill out the logs for fear of re-exposure. For these reasons, not to mention the specialized staff training and time for repeated clinic visits, image rehearsal therapy has low potential to have a large population-level impact on PTSD-related nightmares.

### **NightWare Digital Therapeutic**

For the purposes of this study, we will be using only the Apple (Cupertino, CA) 3rd generation smartwatch and the Apple iPhone. As described above, the NW System consists of a Smartphone (a functionality-limited iPhone), Smartwatch (a functionality-limited Apple Watch 3) and proprietary software application. NOTE: Since the phones and watches will be provided to research staff PRE-IMAGED and with much of the functionality disabled, they will be referred to throughout this document as “research equipment, research phone, and/or research watch”. The NW System has been effective in focus groups when used on both Apple smartwatches and Motorola smartwatches. The NW System utilizes physiological markers obtained via the smartwatch to determine, by proprietary algorithm, whether a subject is in the early stages of a nightmare but has not yet awoken in distress. As directed by the algorithm, the smartwatch then applies varying degrees of vibratory stimulation to the wrist over variable lengths of time with the intention of arousing the subject from sleep without eliciting an awakening.

There are three levels of intervention:

Low: Vibration is least intense, of short duration.

Medium: Vibration is slightly higher, duration is short (same as for “low”).

High: Vibration level is the same as for “medium, duration is increased.

The threshold for these interventions can be manually titrated, if needed, in response to a specific person’s symptoms.

Background information regarding sleep patterns: Sleep architecture has been explored extensively by the use of EEG’s (Electroencephalography). Normal sleep physiology includes micro-arousals. These micro-arousals consist of EEG shifts of the brainwaves to a higher frequency and last from 3-10 seconds. They can be elicited through environmental stimuli such as noise. No definitive limits have been defined as to what is considered a pathologic frequency of micro-arousals. However, during routine clinical practice, micro-arousals of up to 15 times per hour are considered to be within normal limits.

EEG shifts lasting ten seconds, or more are considered **brief awakenings**.

The NW System cannot be used for detection of brain waves, therefore, no brainwave data (EEG) will be collected or analyzed.

Every person has their own sleep pattern that is almost as unique as a fingerprint. The NW System adjusts to a person’s usual sleep pattern by going through an observation-only calibration stage. Usual sleep information is gathered during the first 500 minutes of sleep after the person begins wearing the NW System. The system then calculates an individual “arousal index” based on that sleep information for each subject. Once this arousal index has been calculated, the NW System goes into Active Treatment mode. Every time the arousal index for that person is exceeded, the system will intervene by applying a vibration through the smartwatch. The system uses only enough intervention (see intervention levels, above) to generate a micro-arousal and bring the person out of the nightmare.

In a 2004 study measuring EEG sleep changes elicited by vibratory tactile plus simultaneous auditory stimuli, microarousals were significantly more frequent than awakenings. This suggests that non-painful tactile stimuli can be used to elicit arousals and shift sleep stages without awakening subjects.

The vibrations (0-3 seconds) being delivered by the NW System are intended to be brief enough that they reduce the chances of awakenings and the subsequent memories of the stimulation. The subject continues sleeping, and the smart watch arousal derails the generation and processing of the potential nightmare. Even in the uncommon event that the subject is awakened briefly, nightmare processing should still be curtailed.

Our hypothesis is that by abating these nightmare events people can improve the sleep quality and overall quality of their lives without major adverse consequences.

## 2.3. NW System Description

The NW System’s proprietary application directs the smartwatch to monitor the wearer’s movements and heart rate during sleep to detect the onset of a nightmare. When physiologic symptoms of a nightmare are detected (increased movements, fast movements, increased heart rate), the smartwatch provides gentle stimulation to minimally arouse but not fully awaken the wearer and therefore prevent the nightmare from fully developing and causing significant awakenings and/or sleep disturbance.

Once the smartwatch has been properly fitted to the individual and activated the Active System goes through a learning phase/calibration period. During this time the system monitors the subject's movements and heart rate to delineate the usual low, medium, and high-stress points, termed the "stress index" (threshold) (i.e. system determines the wearer's usual sleep patterns). The application then calculates the "stress index" (threshold) for that individual. When the upper end of this "stress index" (threshold) is exceeded, the system is activated and directs the smartwatch to gently vibrate leading to a slight arousal of the subject to interrupt the development of the nightmare without waking them and allow for a more restful sleep. The Sham System monitors the wearers' sleep patterns and calculates a "stress index" (threshold) but does NOT provide any interventions. The calculated "stress index" (threshold) will be used for subsequent data analysis only. The stress index (threshold) will be set manually on the Sham System to be so high that it will NEVER be activated. Data is collected throughout, and a stress threshold is initially calculated during the initial phase, though the subject isn't aware of this or shown it in any way. The stress threshold is continually calculated in both groups. The sham group never receives treatments regardless of stress threshold

Graphically, this learning/intervention strategy for nightmares is shown below (Active System, only).

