Study Population:	480 potential participants will be screened and 240 adults (120 in each arm), equal to or over the age of 22 years with symptoms indicative of PTSD and related nightmares will be enrolled into the study protocol. This is a multi-site study and will include active-duty military members, military veterans, and military family members.
Planned Number of Sites:	This study will be conducted at WRNMMC and FBCH as the two DoD sites. It is also conducted at multiple VA Hospitals.
Description of Study Intervention:	Wearable digital therapeutic system that will measure physiologic data when worn during sleep to deliver a mild vibration via the watch (i.e., haptic feedback) to elicit an arousal thereby disrupting nightmares. This detection and stimulation sequence will be performed according to NW's proprietary algorithm.
Participant Duration:	30 days in a randomized control trial followed by an additional 60-day open label extension.
Data Banking	De-identified data generated from this study will be saved for use in future studies. The site will transfer data to NightWare that does not contain individual identifiable information.

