## 1.2. Schematic

### 1.3. Schedule of Activities

Study Activities Table:

Study Activity	Pre-Tx	Visit 1	Calibration	Start Up Call	Help Calls	Check Up Call 1	Assessment Call	Check Up Call 2	Visit 2	Visit 3	Visit 4
Study Day	Before Day 0	Day 0	Days 0-3	Day 1	Days 2-6 (Optional)	Day 7	Day 14 (+/-3)	Day 21 (+/- 2)	Day 30 (+/- 7)	Day 60 (+/- 7)	Day 90 (+/- 7)
Recruitment	X										
Chart Review	X										
Phone Screen	X										
Inclusion/Exclusion	X	X									
ICF and HIPAA		X									
Modified Dysken I		X a									
AUDIT		X b									
DAST-10		X c									
Demographics		X									
Medical History		X									
Blood Pressure		X							X		
Med Reconciliation		X							X	X	X
PSQI		X					X		X	X	X
PSQI-A		X							X		
ESS		X							X	X	X
ISI		X							X	X	X
PCL-5		X					X		X	X	X
CAPS-5		X									
VR-12 (QOL)		X							X	X	X
TRNS		X							X	X	X

FOSQ-10		X							X		
PHQ-9		X					X		X	X	X
C-SSRS Lifetime		X							X	X	X
Blinding Assessment Questionnaire									X		
NW Likert Scale		X							X	X	X
Daily Use Questionnaire (Days 1-90)				X	X	X	X	X	X	X	X
Calculate Cutoffs/Eligible ?		X									
Dispense NW Devices		X									
Train Subject		X									
Activate Devices		X									
C-SSRS Since Last Contact									X	X	X
Payment of Subject(Bi weekly)	See Reimbursement Section 6.15										
Start Up Call				X							
Calibration			X								
Active/Sham Treatment			Post- Calib. f								
Help Calls Questionnaire (Optional)					X	X		X			
Checkup Phone Call						X		X			
Sham Cross- over to Active Treatment									X		

a—Administered DURING informed consent process to ensure subjects are capable of consent. Subjects must get all responses correct to be enrolled into the study, b-Exclude if score is equal to or greater than 8. c-Exclude if score is greater than 2. f-Only the Active System goes through calibration and on to Active Treatment.

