### **6.5. Calibration of System (Days 0-3, approximately)**

Once the NW Active System has been installed on the watches of those participants randomized to receive study intervention, a calibration period consisting of the recording of approximately 500 minutes of normal (non-intervention) sleep will occur. This calibration allows for a Stress Index (Threshold) to be assigned for the participant. Sham Systems will not go through a calibration phase, nor will they ever provide study interventions.

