### **6.6. Treatment Operation (Study Intervention, Post-Calibration, Daily Use Questionnaire )**

After the calibration period, the Active System enters active treatment (study intervention) on approximately days 2-3. The Sham System will never go into this mode. Subjects will also receive a daily use questionnaire Deployed via RedCAP

1. RedCAP deployed Daily Use questionnaire (Day 1-90)
  - a. How was your sleep quality? 0 = Refreshing, 1 = Average, 2 = Poor
  - b. Was the device disruptive? 0 = Did not feel it, 1 = Mildly disruptive, 2 = Uncomfortable
  - c. How many nightmare-related awakenings? 0 = none, 1 = 1-2, 2 = 3 or more

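### Sham crosses to Active at Visit 2, but the text says sham is never treated, the visit lists no switch step, and the arm analyses are not stopped at Day 30

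*Protocol*

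**What the plan says.** **The switch.** The Schedule of Activities (Protocol 1.3) has a row "Sham Cross- over to Active Treatment" with a single mark under Visit 2. The synopsis gives participant duration as "30 days in a randomized control trial followed by an additional 60-day open label extension". The synopsis does not say that sham participants become active in the extension; in the text supplied, only the schedule row does.

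**Sham exposure elsewhere.** Section 2.3 says "The sham group never receives treatments regardless of stress threshold". Section 6.5 says "Sham Systems will not go through a calibration phase, nor will they ever provide study interventions". Section 6.6 says of active treatment mode, "The Sham System will never go into this mode". Footnote f of the schedule says "Only the Active System goes through calibration and on to Active Treatment". None of these is limited to the first 30 days.

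**Visit 2.** Section 6.12 lists the questionnaires, the blinding questionnaire, blood pressure, height and weight, and medication reconciliation. It lists no switch and gives no order relative to the assessments. It allows assessment by phone or mail, recorded as a deviation. The only device programming that section 7.1 places in time is the initial one, before the participant first gets home.

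**Analyses.** The primary hypothesis (7.2) and the outcomes in the synopsis and section 3 are set at Day 30. The between-group repeated-measures ANOVA (7.6 and the SAP) covers all surveys and names no study days. The time-to-event analyses (7.2, 7.6 and the SAP) list visits up to Day 90 and do not name arm as a factor. None of this text says how data after the switch are handled.

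**The concern.** After Visit 2 there is no untreated control. A between-arm result that uses Days 60 and 90 compares early with delayed start, not active with sham. Two misreadings follow. If former sham participants improve, a contrast of levels or a hazard ratio by arm shrinks, and a real benefit could be reported as not lasting. A significant group-by-time test could come from sham catching up, yet be read as a difference from an untreated control or as the active benefit fading.

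The wording adds a practical problem. Someone working from 2.3, 6.5 and 6.6 would not expect a switch, and someone following 6.12 would not make one. Where the Day 30 questionnaires come by phone or mail, no step requires them to be complete before the unit is switched.

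**Working it through.** **1. The plan's own figure.** Inputs from section 7.3: 60 completers per arm, difference 3 points, SD 5, two-sided 0.05 (7.2).
- SE = 5 × √(2/60) = 0.913; noncentrality = 3 / 0.913 = 3.29.
- Power from the noncentral t with 118 df = 90.3%. The stated 90% reproduces, and nothing below changes it.

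**2. Assumptions for Days 60 and 90.** The documents give neither the catch-up of former sham participants nor the within-person correlation. I take catch-up c = 0, 0.5 or 1 (the share of the 3 points gained by Day 60 and held) and correlation ρ = 0.5 or 0.7 between change scores. The plan does not name the first two contrasts below; they show what a level comparison by arm would do.

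| Contrast | Difference | SE | c = 0 | c = 0.5 | c = 1 |
|---|---|---|---|---|---|
| Single visit, Day 60 or 90 | 3(1 − c) | 5√(2/60) | 3.0 points, 90% | 1.5 points, 37% | 0 points, 5% |
| Mean of Days 30, 60, 90 | 3 − 2c | 5√((1 + 2ρ)/3) × √(2/60) | 3.0 points, 95–98% | 2.0 points, 68–76% | 1.0 point, 23–27% |

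Percentages are power; ranges run over ρ.

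**3. Group-by-time test with baseline included.** This is closer to the planned ANOVA, because Day 0 is one of the time points. I assume raw scores at Days 0, 30, 60 and 90, compound symmetry, and change SD 5, so the within-person error variance is 25/2 = 12.5. The arm differences are (0, 3, 3 − 3c, 3 − 3c). Noncentrality λ = (60/2) × SS / 12.5, where SS is the sum of squares of those four differences about their mean; F has 3 and 354 df.
- c = 0: (0, 3, 3, 3), SS = 6.75, λ = 16.2, power 93%.
- c = 0.5: (0, 3, 1.5, 1.5), SS = 4.5, λ = 10.8, power 79%.
- c = 1: (0, 3, 0, 0), SS = 6.75, λ = 16.2, power 93%.

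The overall test has the same power when the benefit persists against an untreated control (c = 0) as when sham has fully caught up (c = 1). Its p-value does not tell the two apart.

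**4. Hazard ratio, if arm were the Cox covariate.** Simulation of the first 3-point decrease at Days 30, 60 or 90 (6,000 per arm, Efron ties, assumed mean sham improvement 0, 2 or 3 points, ρ 0.5 and 0.7): about 1.7–2.1 at c = 0, 1.5–1.7 at c = 0.5 and 1.3–1.4 at c = 1.

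**5. Exposure after the switch.** At Day 60, former sham participants have had about 27–30 treated nights (30, less up to 3 if recalibrated) and active participants 57–58 (60 less 2–3). At Day 90 the figures are 57–60 and 87–88.

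**The case against.** The strongest reply is that the intent is clear. The synopsis ends the randomised trial at 30 days, and the primary and listed secondary outcomes are at Day 30. Sections 2.3, 6.5 and 6.6 can be read as describing the sham configuration rather than the person's whole course. Section 6.4 treats sham and active as a mode set remotely, so a cross-over is only a mode change. This stands: a reader might infer that nothing in the documents ends the randomised period at Day 30, and the synopsis says otherwise. The remaining gap is that no analysis text carries that limit, and that 2.3 speaks of the sham group, not the sham mode.

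The order at Visit 2 also carries little risk for participants seen in person. The device acts during sleep, so no treated night can fall between a switch and questionnaires completed at the same visit. Phone or mail completion is the exception.

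The later analyses are loosely specified: Kaplan-Meier and Cox models are optional, and arm is not named. The sizes above therefore apply only if arm comparisons are drawn from those analyses. PSQI-A and FOSQ-10 are not collected after Day 30 and cannot be affected.

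Section 2.3 says "The stress threshold is continually calculated in both groups", section 2.2 says "Usual sleep information is gathered during the first 500 minutes of sleep after the person begins wearing the NW System", and 6.5 denies sham a calibration phase. Which threshold a switched unit uses is therefore unstated, but this is an operational clarification for the open-label phase only. The schematic in 1.2 is not in the text supplied, and its absence is not counted against the plan.

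**Conclusion.** The point holds as a gap in wording, procedure and analysis scope. The schedule switches sham to active at Visit 2, four places say without time limit that sham is not treated, 6.12 has no switch step, and the ANOVA and time-to-event text does not separate the randomised from the open-label period.

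The consequence is confined to arm comparisons that use Days 60 and 90. At an assumed 50% catch-up, a single-visit contrast drops from 3.0 to 1.5 points and power from 90% to about 37%. A group-by-time test keeps 79–93% power under the stated assumptions, and there the danger is misinterpretation.

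Two stronger readings are not supported. One is that the Day 30 result is compromised: the primary test and its 90% power are unaffected when the assessments precede the switch, and the one-sample safety tests in 7.5 concern the active system only. The other is that every arm contrast is pulled toward no difference: that is true of level contrasts and hazard ratios if sham improves, but not of the interaction test. Catch-up, correlation and sham improvement are assumptions throughout.

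**What to change.** 1. In 7.2, 7.6 and the SAP, limit randomised between-arm inference to Day 30, including the ANOVA and time-to-event analyses. For the latter, censor at the switch or use the proportion with a 3-point decrease by Day 30. Report Days 60 and 90 as open-label and descriptive, with the arms labelled early and delayed start.
2. In 2.3, 6.5, 6.6 and footnote f, limit the never-treated wording to the 30-day randomised period.
3. In 6.12, add a remote switch made only after all Day 30 assessments are complete, including those by phone or mail. The remote mode setting in 6.4 and 7.1 can be used. State the threshold rule for switched units in the same step.

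Cost: a wording amendment, one procedural step and one analysis sentence, with no change to sample size. The plan gives up a confirmatory arm test at Days 60 and 90, where no untreated control remains. The Day 30 responder proportion should stay secondary. With normal changes, SD 5 and assumed mean sham improvement of 0–3 points, it compares 27% with 50%, up to 50% with 73%. With 60 per arm its power is about 72–74%, against 90% for the mean.

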**Figure 2: NightWare User Interface and Data Flow**

### Active Intervention Description

The Active System captures heart rate and movement data from the wearer via sensors in the smartwatch (gyroscope, accelerometer, and heart rate monitor). This data is transmitted to the smartphone where the proprietary NW application algorithms calculate the individual's stress index (threshold) and learn how best to intervene in that person's nightmare development. This data is also transmitted by the smartphone to the secure NW server. This data is accessible only to NW Study staff and is used to monitor each subject. Monitoring will be used to ensure that each subject is wearing the NW System every night and to manually change the titration threshold and intervention strength parameters as necessary to provide the best sleep possible. If the subject is not wearing the NW System every night, the subject will be contacted to ask why the NW System is not being utilized. The Sham System will also be monitored to ensure that the system is being used nightly, but as the system is NOT active, no changes to the parameters will be made.

